5.2. Eligibility Criteria

Participants have to complete a set of questions (in REDCap) during the screening process. They will be instructed to consume no alcohol and no more caffeine than usual 24 hours before each study visit.

5.2.1. Inclusion Criteria

In order to be eligible to participate in this study, an individual must meet the following criterium:

- >50 years old

5.2.1. Exclusion Criteria

Any individual who meets one or more of the following criteria will be excluded from participation:

- Implanted device or metal in head (including cochlear implant or other hearing aid), cardiac pacemaker or any other powered medical device
- Known neurological disease from history (epilepsy, sleep disorder (insomnia, sleep apnea, restless legs syndrome, parasomnia), stroke or transitory ischemic attack, cognitive impairment, neurodegenerative disease (for example Alzheimer's disease, Parkinson's disease or amyotrophic lateral sclerosis), immune-mediated disease of the central nervous system, chronic infectious brain disease, brain tumor, traumatic brain injury with loss of consciousness and/or intracranial bleeding, chronic pain with the need for daily analgesic use)
- Positive screening for epilepsy (questionnaire)
- Pathological Montreal Cognitive Assessment (MoCA $<26/30$ points)
- Brain surgery in the past (lifetime)
- Known psychiatric disorder from history (schizophrenia (lifetime), obsessive compulsive disorder (OCD; lifetime), borderline personality disorder (lifetime), anxiety disorder (lifetime), bipolar disorder (lifetime), psychosis (lifetime), eating disorder (lifetime), depression (within the last three months))
- Positive screening for anxiety disorder (GAD-7 $\geq 10/21$ points) or positive screening for depression (PHQ-9 $\geq 5/27$ points)
- Known other relevant medical condition from history (moderate to severe chronic obstructive pulmonary disease (COPD), abnormal kidney function (defined as estimated Glomerular Filtration Rate $<60\text{ml}/\text{min}$), current liver disease (defined as hepatitis and/or liver cirrhosis), cancer, diabetes mellitus, cardiac disease (heart failure, myocardial infarct, atrial fibrillation and revascularization – all within the last three months))
- Working in night shifts or going to bed after midnight on 3 or more nights per week
- Positive screening for sleep disorder (PSQI $>5/21$ points)

- Psychotropic treatment or illegal drugs (including cannabis) within the last three months
- Indication for alcohol use disorder: AUDIT score (Alcohol Use Disorders Identification Test; screening for unhealthy alcohol use) ≥ 7 for females and for males ≥ 65 years or ≥ 8 for males <65 years
- Not willing to abstain alcohol at least 24 hours before each study visit
- Women who want to become pregnant, are pregnant, plant to seek or are seeking fertility treatment

5.3. Enrollment/Selection Strategies

5.3.1. Prospective Recruitment

We will advertise the study directly to the public on websites such as ClinicalTrials.gov, studypages.com, Research For Me, frohlichlab.org and Carolinaneurostimulation.org. We will have contact information and a summary of the clinical trial posted on the [name] Lab Facebook and Twitter pages. We will also be launching a Facebook or Instagram advertisement to identify potential participants. Furthermore, we will also be using the UNC Mass email and department listserv to send out an email containing the advertisement. In addition, we will post fliers senior living communities. We have previously recruited about 50 participants from an identical population within 3 months.

We will send unencrypted emails to facilitate the initial contact to potential participants. Medical information is never requested per email. All medical information is recorded through HIPAA conform Zoom meetings and REDCap surveys.

The advertisement will include a link to a brief prescreening survey on REDCap to help identify participants. Interested individuals can then either visit the specified website and complete an online screening survey on REDCap or call or email to register for a telephone prescreening. All participant identifiers will be stored in REDCap and password encrypted tables stored on UNC servers until recruitment is over. When recruitment is over, all patients who do not consent or are not eligible for participation in the study will have their responses permanently deleted.

Our retention strategy includes a payment schedule of two times \$50 per participants. Thus, completion of the study will result in a financial compensation of \$100.

5.3.2. Screen Failures

In the case that a participant enrolls in the trial and the screening reveals that they do not meet study criteria, the study personnel completing the interviewing process will clearly explain why the participant does not meet criteria. If a time-sensitive criterion is not met, re-screening may occur at a later time. In the worst case, we expect only $\sim 25\%$ of those interested to be eligible.

5.4. Strategies for Retention

Due to the low time burden (five study visits on site) at short intervals (maximum two weeks), we expect a low drop-out rate. Nevertheless, we are capturing data on possible reasons in case of discontinuation.

5.5. Matching and Stratification

Not applicable.

5.6. Randomization and Concealment

Participants will be assigned to active stimulation first or sham stimulation first using simple randomization.

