2.2. Scientific Rationale

This controlled cross-over pilot study will be used to prepare for a full-scale RCT in patients with mild cognitive impairment by investigating feasibility as well as acceptability and adherence of the study procedures in a sample of n=28 healthy elderly adults. Any effect on memory performance and sleep EEG will be documented but is not a requirement for the development of an RCT. We include people over 50 years of age because memory problems and neurodegenerative diseases (specifically Alzheimer's Disease) occur in the second half of life. The exclusion criteria are designed to ensure that people are not cognitively impaired by a disease of the brain or other impairment of bodily functions. In addition, we exclude contraindications to tACS.

The pilot study serves as a basis for the application of the technique in specific patient groups, in particular those with mild cognitive impairment.

3. Specific Aims

3.1. Aim 1

To establish acceptability of cognitive testing during tACS in healthy elderly participants. The threshold is set to 80% of participants.

3.2. Aim 2

Evaluation of an effect of a single session of gamma-tACS on memory (a) and associative memory (b) performance compared with control tACS. The estimand of interest is the comparison of the individual results of the memory tests at the individual and at the group level (paired t-test or a non-parametric test, respectively), for delayed (immediately after stimulation) and ultra-delayed recall (after a night of sleep as well as after 5 days).

3.3. Aim 3

Feasibility (a) and acceptability (b) of an ambulatory single-channel EEG device. The estimands of interest are the proportion of participants with at least four hours of recording in the first night (a) and the proportion of participants with three nights of at least 4 hours of EEG data (b).

3.4. Aim 4

The comparison of specific sleep EEG features, i.e. sleep spindles (a) and slow wave sleep (b), which are both prominently associated with cognitive functioning, especially memory processes, after each stimulation condition. Comparison will be on individual and on group level (via t-test or a non-parametric test, respectively).

3.5. Aim 5

To investigate whether there is a correlation between the effects of tACS (versus control control tACS) on memory recall and memory-associated sleep EEG features (especially amount of sleep spindles and slow wave sleep) on an exploratory level.

3.6. Aim 6

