4.2. Experimental Design

This is a controlled cross-over study. Participants will be randomly allocated to the respective sequence (first tACS, then control stimulation – vice versa) via simple randomization, i.e. based on a single sequence of random sequence numbers generated by computer.

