5.1. Numbers of Participants

5.1.1. Number to be screened: $N \leq 100$

5.1.2. Number to be enrolled: $N \leq 50$

The sample size is 28 participants in the final dataset, i.e. the participants who completed all the visits for the primary outcomes, i.e. Visits 1, 2, 3, 4, 5, 6, 7 (including the three nights with EEG). However, to ensure that 28 participants complete the experiment, we conservatively estimate to screen 100 participants and to enroll 50 participants as a ceiling for the sake of IRB approval. The motivation for the sample size of 28 participants is the following power analysis: power analysis: $dz = 0.5$, $1-\beta = 0.80$, $\alpha = 0.05$. Participants who drop-out or have missing data will be replaced.

Recruitment takes place in the general population.

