Visit 5 (6-9 days after Visit 2; afternoon/early evening, i.e. start between 12pm and 6pm)

The day before: reminder (e-mail/SMS/phone call, depending on the participant's preference) of appointment on the following day - including request to abstain from alcohol and drugs as well as from excessive caffeine consumption.

1. Questioning whether there has been any use of alcohol, psychotropic substances or illicit drugs during the past 24 hours. If yes, the participant is excluded.
2. Questioning if there is a new diagnosis. If yes, the participant will be excluded if the diagnosis meets exclusion criteria.
3. Questions to assess current sleepiness and mood, as this may affect the results of further testing:
 - 3.1 Questions for sleep quality the night before
 - 3.2 Karolinska Sleepiness Scale
 - 3.3 Positive And Negative Affect Schedule (PANAS)
4. Gamma-tACS or controlstimulation (according to randomization) during the following cognitive tests, presented on a computer screen (2 minutes of resting EEG without stimulation after each test):
 - 4.1 Rey Auditory Verbal Learning Test (RAVLT, version 2)
 - 4.2 Letter Fluency; letters F, A, S

- 4.3 Stroop Color and Word Test
- 4.4 Trail Making Test A and B
- 4.5. Word association test; version 2
- 4.6 Four subtests of the Test of Attentional Performance (TAP): Alertness, Go/NoGo, Divided Attention, Visual Scanning
- 4.7 RAVLT delayed recall; version 2
5. Evaluation of side effects with open question (“Did you feel anything particular or note anything special during this session?”)
6. The participant will be given the sleep diary for the third night with the EEG headband.

Visit 6 (day after Visit 5; morning, i.e. start between 8am and 12pm)

1. The participant brings back the EEG-headband (used the night before). Data quality check, review of sleep diary.
2. Questioning whether there has been any use of alcohol, psychotropic substances or illicit drugs during the past 24 hours. If yes, the participant is excluded.
3. Questions to assess current sleepiness and mood, as this may affect the results of further testing:
 - 3.1 Questions for sleep quality the night before
 - 3.2 Karolinska Sleepiness Scale
 - 3.3 Positive And Negative Affect Schedule (PANAS)
4. Cognitive follow-up testing
 - 4.1 RAVLT “ultra-delayed” recall; version 2
 - 4.2 Letter fluency; letters B, H, R
 - 4.3 Stroop Color and Word Test (SCWT)
 - 4.4 Trail Making Test Part A and B
 - 4.5 Word association recall; version 2

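### Simple randomisation leaves the balance of the two crossover sequences to chance, while list version is tied to period and no planned analysis clearly adjusts for period

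*Combined protocol and SAP*

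**What the plan says.** **Allocation.** Section 5.6: "Participants will be assigned to active stimulation first or sham stimulation first using simple randomization". Section 4.2 adds that this is done "via simple randomization, i.e. based on a single sequence of random sequence numbers generated by computer". Section 5.5 declares matching and stratification not applicable. No blocking or other balance constraint is described, and the allocation ratio is not stated.

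**Numbers.** Section 5.1.2: "The sample size is 28 participants in the final dataset", with up to 50 enrolled to obtain them. The same section says "Participants who drop-out or have missing data will be replaced", without saying to which sequence the replacement goes.

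**Test material.** In section 7.4 every participant gets version 1 of the RAVLT and of the word pairs at Visit 2, whichever stimulation comes first. At Visit 5 every participant gets version 2: "Rey Auditory Verbal Learning Test (RAVLT, version 2". Letter Fluency at these visits uses the same letters both times, and Stroop, Trail Making and TAP are also repeated in both periods.

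**Analysis.** The document names two.
- Section 3.2 (Aim 2) gives a "paired t-test or a non-parametric test, respectively". Section 3.6 (Aim 6) gives the same choice, and section 3.4 (Aim 4) a t-test or non-parametric alternative. None has a period term.
- The synopsis gives ANCOVA for Aims 2, 4 and 6. Section 8.3 specifies, for next-day recall, a repeated-measures ANCOVA with time (before and after treatment) and treatment as within-subject factors and stimulation order as covariate. It carries this method to Aim 4 and gives ANCOVA for Aim 6. Again no period term is named.

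**The concern.** In a two-sequence crossover, period effects cancel from the simple mean of within-person differences only when the sequences are equal in size. Here period carries practice on the repeated tests and any difference in difficulty between the two lists, because list version never varies within a period. Simple randomisation of a sample this small often gives unequal sequences.

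If the analysis has no period term, the imbalance moves part of the period effect into the treatment estimate of the one trial that is run. If it has one, the estimate is protected and only precision is lost. Which case applies depends on whether section 3 or section 8.3 governs, and on how order enters the model in section 8.3.

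**Working it through.** **Inputs.** N = 28 completers, dz = 0.5, power 0.80, alpha 0.05 (section 5.1.2); two sequences, 1:1 assumed. The period effect π (second minus first) is not in the documents. I assume a range of 0.25 to 1.0 SD of the paired difference.

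**1. The plan's own figure.** For a paired t-test by the exact noncentral t, one-sided alpha 0.05 needs N = 27, and 28 gives power 0.825. Two-sided needs N = 34, and 28 gives 0.723. So 28 is reproduced closely only as a one-sided calculation; sidedness is not stated.

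**2. Chance of imbalance.** P(k : 28−k or worse) = 2 × Σ C(28, j) / 2^28 for j ≥ k. For k = 18 this is 2 × 24,821,333 / 268,435,456 = 0.185. An exact 14:14 split has probability 0.149.

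**3. Without a period term.** A gamma-first person's difference is τ − π in expectation and a control-first person's is τ + π, so the mean is τ + π × (n_control-first − n_gamma-first)/28. At 18:10 the share of π carried over is 8/28 = 0.286. The average over all splits is 0.149.

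**4. With a period term.** The estimate is the average of the two sequence means. Its relative information is 4·n1·n2/28². At 18:10 this is 720/784 = 0.918, and at 19:9 it is 684/784 = 0.872. The expected loss is E[(n1−n2)²]/28² = 28/784 = 3.6%.

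| Split | P(this or worse) | Share of π carried, no period term | Information lost, with period term | Two-sided power at dz = 0.5, with period term |
|---|---|---|---|---|
| 14:14 | – | 0 | 0 | 0.721 |
| 16:12 | 0.572 | 0.14 | 2% | 0.713 |
| 18:10 | 0.185 | 0.29 | 8% | 0.685 |
| 19:9 | 0.087 | 0.36 | 13% | 0.662 |

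**5. Consequence at a realised 18:10 split** (100,000 simulated trials, two-sided tests; the power columns take the imbalance to work against gamma):

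| Assumed π (SD) | Shift = 0.286 × π (SD) | Type I error, no period term | Power, no period term | Power, with period term |
|---|---|---|---|---|
| 0.25 | 0.07 | 0.059 | 0.57 | 0.69 |
| 0.5 | 0.14 | 0.077 | 0.36 | 0.69 |
| 1.0 | 0.29 | 0.103 | 0.05 | 0.69 |

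Averaged over all random splits, the unadjusted type I error is about 0.051 for each π. Unadjusted power is 0.70, 0.63 and 0.44, against 0.72 with no period effect.

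**6. What the order covariate does.** Order is constant within a person, so an additive order term cannot change a within-person contrast. In one simulated 18:10 data set the raw paired difference was −0.015, and it was still −0.015 with additive order. A period term gave 0.066, as did treatment crossed with centred order. Treatment crossed with order coded 0/1 gave 0.353, which is the effect in the control-first sequence alone.

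**7. Balance alone.** At 14:14 with π = 0.5 SD, the unadjusted paired t-test has no bias but leaves period variance in the error: type I error 0.028 and power 0.64, against 0.72 with a period term.

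**The case against.** The strongest reply is that section 8.3 is the analysis section and includes stimulation order, so the simple tests in section 3 may not be what will be run. If order is crossed with treatment and centred, the period effect is removed and little remains to complain of: the split is 16:12 or better in 66% of trials (1 − 0.345), at a cost of at most 2% of the information. This stands, and it rules out saying that the memory analysis is biased. It does not close the point. Section 8.3 does not say whether order is additive or crossed, or how it is coded. Its time factor is before versus after treatment, not first versus second period. The allowance in section 8.1 for additional covariates commits to nothing, and section 3 still names the unadjusted tests.

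A reader might infer that replacing dropouts worsens the imbalance. If dropout is unrelated to sequence, the 28 completers still split as Binomial(28, 0.5). A simulation with 30% dropout and replacement again gave about 18% for 18:10 or worse. Only sequence-dependent dropout would change this, and nothing in the documents suggests it.

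The stakes are also limited. Section 2.2 says that an effect on memory or sleep is not a condition for the later RCT, and the feasibility proportions of Aims 1 and 3 do not depend on sequence balance. Even so, section 8.3 labels next-day recall a primary outcome and states a hypothesis for it.

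**Conclusion.** The point holds as a low-cost design improvement joined to an analysis gap. Chance imbalance of 18:10 or worse has probability 18%. At 18:10, 29% of any period or list effect enters a comparison with no period term. Over the assumed range of 0.25 to 1.0 SD that is a shift of 0.07 to 0.29 SD, against a planned effect of 0.5 SD. With a period term only precision is lost.

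Three stronger readings are not supported. First, simple randomisation does not inflate the type I error of the design; the inflation appears only conditionally on a poor split. Second, no shift in words recalled can be stated, because the documents give neither a period effect nor a list difference. Third, blocking would not be enough: it balances those randomised (up to 50), not exactly the 28 completers, and an unadjusted test still loses power at 14:14.

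The conclusion assumes 1:1 allocation and dropout unrelated to sequence. The error rates and powers also depend on the assumed range for the period effect.

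**What to change.** 1. In sections 4.2 and 5.6, replace simple randomisation with 1:1 computer-generated permuted blocks of varying, concealed size for the two sequences.
2. If replacements are to take the sequence of the person replaced, have this done only by an unblinded list holder with no participant contact. Section 6 says that visual side effects differ by frequency, so staff who guess a dropout's sequence could otherwise know the replacement's, which would undermine the double blind in section 5.7.
3. For Aims 2, 4 and 6, name one model with treatment, period and participant, in place of the conflicting tests in sections 3.2, 3.4, 3.6 and 8.3. List difficulty is then absorbed by the period term.

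Costs: a new allocation list, slight predictability of replacement allocations, and one degree of freedom for period (two-sided power at 14:14 is 0.721 instead of 0.723). Balance among completers will be near, not exact. No extra participants are needed.

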5.7. Blinding

This is a double-blind study. Both participants and research staff will be blinded to the stimulation condition.

6. Treatment Design: Procedures

Description

Transcranial alternating current stimulation (tACS)

Participants will be stimulated with the commercial, CE-certified Neuroconn multiple channel (MC) stimulator. The use of this device routinely received a non-significant risk (NSR) designation on review by the full UNC IRB. The NeuroConn device description is as follows: The DC-STIMULATOR MC is a CE-certified medical device for conducting non-invasive transcranial current stimulation in humans. The DC-STIMULATOR MC is a micro-processor-controlled current source. It meets the highest safety standards thanks to (hardware- and software-based) multistage monitoring of the current path. By continuously monitoring electrode impedance it can detect insufficient contact with the skin and automatically terminate stimulation, maximizing patient safety. The device includes a digital display with various stimulation modes to be selected and stimulation parameters such as current strength, duration, fade-in and fade-out to be set.

DC-STIMULATOR MC features:

- 4 programmable, micro-processor-controlled constant current sources using 25 independent channels (optional: 16 channels)
- For transcranial direct current stimulation (tDCS), transcranial alternating current stimulation (tACS), cranial electrical stimulation (CES), galvanic vestibular stimulation (GVS) and transcranial random noise stimulation (tRNS)
- 4 standard modes – tDCS (continuous stimulation) – pulse (cyclical stimulation activation/deactivation) – sinus (sinus wave) – noise (normally distributed)
- Current strength and curve forms adjustable up to $\pm 4,000 \mu\text{A}$, AC current strength adjustable up to 8,000 μA (peak-to-peak)
- Frequencies adjustable up to 1,000 Hz, phase freely adjustable

Electroencephalography (EEG):

A high-density EEG net (128 electrodes including electrooculography electrodes; EGI, Inc.). Continuous qEEG recording will be performed. Sampling rate during the continuous recording will be 1 kHz with Cz as the reference and a channel between Cz and Pz as ground, using an EGI system with SDK AmpServer Pro (Geodesic, Eugene, Oregon).

Transcranial magnet stimulation (TMS) motor thresholding:

Additionally, TMS motor thresholding (M. interosseus dorsalis I, with EMG electrodes) will be performed, as there is evidence suggesting a relationship between the effect of tACS and brain excitability measured with single pulse TMS. We therefore measure cortical excitability by performing motor thresholding using single pulse TMS (transcranial magnetic stimulation) during Visit 2. A MagVenture MagPro X100 TMS device will be used.

Dosing and Administration

The research team will first measure each participant's head using the 10-20 system to determine the electrode locations. Participants will then be fitted with the 4 electrodes for stimulation: two 4.5x4.5cm electrodes placed over T7/P7 and T8/P8 (10/20-EEG-system). Electrodes will be carbon rubber, with Ten20 conductive paste applied.

For gamma-tACS 40 Hz will be applied ("natural target value", for a review see (33)). We have decided to apply control stimulation instead of sham stimulation as we have been able to demonstrate visual side effects with bitemporal asynchronous stimulation (i.e. synchronized within one hemisphere) which differ according to stimulation frequency (phosphenes with higher frequencies, sensation of movements of the environment with lower frequencies). Hence, 21 Hz tACS will be applied for control stimulation (reasoning: no known specific effects on temporal lobe; close to gamma-stimulation and hence similar concerning side effects; not a harmonic frequency to 40 Hz). An individual current amplitude will be determined before stimulation (for 21 Hz and 40 Hz; ramp-on 40s, continuous stimulation 20s; from 2mA peak-to-peak in steps of 0.25mA until "symptoms well tolerable for at least

one hour". The lower of the two current amplitudes from 40 Hz and 21 Hz will be applied for both stimulation conditions).

For both stimulation sessions, a ramp-on and ramp-off time of 40s will be applied.

Researchers will monitor participants during stimulation. Personnel will be thoroughly trained and have trainings documented on the transcranial stimulation device and will be present during all stimulation sessions. Co-investigator [name] MD is a Swiss board-certified neurologist who will serve as supervisor for the stimulation study visits.

During stimulation, the participants will perform the following cognitive tests presented on the computer screen or on paper: RAVLT (Rey Auditory Verbal Learning Test) (26), a word association test (8 word-pairs), Letter Fluency (28), Stroop Color and Word Test (29), Trail Making Test A and B (30), TAP (Test of Attentional Performance) (31). The stimulator will be triggered by remote control from the experiment script and will administer stimulation during each single test. After each block of stimulation, an eyes-open resting state EEG will be performed. All stimulation involves 20 seconds of ramp-in time and 20 seconds of ramp-out time. The total duration of the stimulation and testing is approximately 40 minutes.

7. Schedule of Activities and Procedures

